4. GENERAL CONSIDERATIONS FOR DATA ANALYSIS

Unless otherwise specified, continuous variables will be summarized by presenting the number of non-missing observations (n), mean, standard deviation, median, 25th percentile, 75th percentile, minimum, and maximum. Categorical variables will be summarized by presenting frequency count and percentage for each category. All tabulations will be based on pooled data across centers. For the summary statistics of all numerical variables unless otherwise specified, minimum and maximum will be displayed to the same level of precision as reported. Mean, median, 25% and 75% quartiles will be displayed to one level of precision greater than the data collected. Standard deviation will be displayed to two levels of precision greater than the data collected.

CTI Clinical Trial and Consulting Services will perform all efficacy and safety statistical analyses using SAS for Windows statistical software, version 9.4 or higher (SAS, Cary, NC), except where other software may be deemed more appropriate.

Subject data will be listed, sorted by subject number.

4.1 Data Quality Assurance

Once all the source verification is complete, all queries are resolved, and the database has been updated appropriately, the database will be locked and made available to CTI Biostatistics for final analysis.

All SAS programs used to create analysis data sets, tables, and listings will be double programmed. The SAS outputs will be compared, and the programs will be updated until the outputs match.

4.2 Analysis Sets

The following analysis sets will be used in the statistical analyses.

Full Analysis Set (FAS): The FAS will consist of all subjects who are enrolled in the study. Subjects are considered enrolled once biopsy is taken.

Injection Analysis Set (IAS): The IAS will include all subjects who receive at least one REACT injection.

4.3 Study Day

Study day 1 will be the day of the first REACT injection. That is, the treatment start date is the date of the first REACT injection. For assessments/events on or after the treatment start date, the

study day is calculated as the date of assessment/event minus the date of treatment start + 1. For assessments before treatment start date, the study day of the assessment is defined as the date of assessment minus the date of treatment start.

4.4 Assessment Windows

No analysis windows are planned for the study regarding data collected outside the protocol specified windows. All data will be included in the analysis based on the visit as it is recorded in the database.

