**Table 1: Time and Events Table**

Abbreviations: AE (adverse event); ConMeds (concomitant medications); DSMB (Data Safety and Monitoring Board); ECG (electrocardiogram); EOS (End-of-Study Visit); I /E (inclusion /exclusion); KDQOL (Kidney Disease Quality of Life Survey); MRI (magnetic resonance imaging); REACT (Renal Autologous Cell Therapy); PE (physical examination).

Notes:

- \* Day 1 follow-up visit should only be conducted if there is a safety event identified during or after the kidney biopsy.
- \*\* Every attempt should be made to ensure the second REACT injection is administered 6 months (+4 weeks) after the first injection. In the event that the subject cannot schedule his/her second REACT injection 6 months after receiving the first injection or cannot keep his/her scheduled 6-month visit, ProKidney and the Medical Monitor must be notified immediately. The expectation is that the subject and the clinical center will accommodate the Sponsor's preference that the series of 2 REACT injections should be administered no more than 6 months apart.
- a. If the screening assessment falls outside of the 60-day window before renal biopsy, re-screening will be performed as described in Screening ([Section 6.1](#)).
- b. Because the second REACT injection will occur 6 months (+4 weeks) after the first injection, the 6-month visit may not be scheduled.
- c. In the event that a second REACT injection will not be administered, the subject will undergo all follow-up assessments after the last REACT injection at the 24-month EOS Visit.
- d. The EOS Visit will take place 24 months after the last REACT injection, or when the subject is terminated from the study by the Investigator ([Section 8.6](#)) or when the subject voluntarily discontinues from the study ([Section 5.4](#)).
- e. The Informed Consent Form must be signed and dated prior to conducting any study-specific procedures, including those at the Screening Visit. Signing the Informed Consent Form starts the 60-day timeline for screening.
- f. The PE and interim PE are described in [Section 7.2.2](#).
- g. Vital signs include heart rate, resting blood pressure, respiration rate, and body temperature. ([Section 7.2.1](#)). At the Pre-Biopsy Visit (Day -3 to Day -1) and the Pre-Injection Visit (Day -14 to Day -10) three BP measurements will be taken and the average will be used to satisfy entry criteria.

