#### 6.6. End-of-Study Visit

This section describes situations in which a subject will undergo the EOS visit; for example, due to premature discontinuation from the study or completion of all protocol-specified follow-up visits.

- If a subject discontinues from the study after undergoing the renal biopsy but before REACT injection, then that subject should complete all EOS assessments except for the MRI and/or renal scintigraphy studies. These imaging studies should only be completed if, in the judgment of the Investigator, one and/or the other would provide critical safety information needed for patient care. If the subject is experiencing an investigational product- or study procedure-related SAE, then the subject will not be discontinued until the SAE has resolved, stabilized, or returned to baseline.
- If a subject discontinues from the study after undergoing one or two REACT injections but before completing all of the protocol-specified follow-up visits, then he/she should have the EOS Visit at the time of discontinuation. For these subjects, the Investigator will determine whether or not it is clinically prudent to perform one or both of the imaging studies (i.e., MRI and renal scintigraphy). If the subject is experiencing an investigational product- or study procedure-related SAE, then the subject will not be discontinued until the SAE has resolved, stabilized, or returned to baseline.
- If a subject completes all of the protocol-specified follow-up visits, he/she will undergo all EOS assessments 24 months after the final REACT injection at the EOS Visit. If the subject is experiencing an investigational product- or study procedure-related SAE, then the subject will not be discontinued until the SAE has resolved, stabilized, or returned to baseline.

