3. INVESTIGATIONAL PLAN

3.1 Study Design

This is a multi-center, prospective, open-label, single-group study. Up to 10 subjects who complete screening procedures and satisfy all inclusion and exclusion criteria specified in the protocol will be enrolled into the study immediately prior to the biopsy. All subjects will be treated with two REACT injections 6 months (+4 weeks) apart after biopsy. Subjects will be followed over a 24 month period post the last injection. See Appendices A-B for the Schedule of Events.

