4.5 Handling of Dropouts or Missing Data

Missing data will remain missing. No imputation of missing data will be performed.

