9. SAMPLE SIZE

Up to 10 subjects who complete screening procedures and satisfy all inclusion and exclusion criteria will be enrolled. Statistical analyses will be primarily descriptive in nature and no statistical hypothesis testing is planned for the study.

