- h. Vital signs (included are heart rate, blood pressure, and respiration rate) will be measured throughout the procedure. Temperature is not required to be recorded throughout the procedure.
- i. Refer to [Table 2](#) for a schedule of laboratory assessments.
- j. Ultrasound will be performed at the Screening Visit to verify subject eligibility and to obtain baseline echogenicity reading. Subsequent Ultrasounds will monitor echogenicity.
- k. Ultrasound will be performed following the in-patient renal biopsy on Day 0 and Day 1, and following the in-patient REACT injection(s) on Day 0 and Day 1 with the aim of monitoring possible, subclinical AEs.
- l. A MRI study without contrast will be performed at the Screening Visit through Day -1 before renal biopsy to determine kidney size and volume.
- m. Renal scintigraphy will be performed before the first REACT injection, before the last REACT injection, at the 6-Month Visit after the last REACT injection, at the 12-Month Visit after the last REACT injection, and at the month 24/EOS Visit.
- n. The REACT preparation will be handled and injected according to procedures described in the Study Reference Manual.
- o. CT Scan must be used in conjunction with ultrasound for the REACT injection procedure.
- p. Subjects may be admitted to hospital per site standard practice. Subjects who do not experience complications may be discharged the same day consistent with site standard practice.
- q. Subjects will undergo a funduscopic exam with retinal photography of both retinae to monitor diabetic retinopathy at screening, month 12, and month 24/EOS visit.

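### One EOS Visit serves both Month 24 and early termination, and SAP 4.4 tabulates by recorded visit, so the Month 24/EOS row can mix follow-up times

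*SAP*

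**What the plan says.** The visit has two triggers. Protocol Table 1, note d: "The EOS Visit will take place 24 months after the last REACT injection, or when the subject is terminated from the study"; the note goes on to add voluntary discontinuation. Section 6.6 applies this to a subject who has had one or two injections and stops early: "then he/she should have the EOS Visit at the time of discontinuation". The SAP appendices repeat note d, and Appendix A, note m, schedules the last scintigraphy "at the month 24/EOS Visit". Neither document describes a separate early-termination visit.

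The tabulation rule is in SAP 4.4, which plans no analysis windows and continues: "All data will be included in the analysis based on the visit as it is recorded in the database". SAP 4.5 adds: "Missing data will remain missing. No imputation of missing data will be performed".

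The tables that depend on the visit label are the by-time-point or by-visit summaries of raw values and change from baseline: renal-specific laboratory values (SAP 6.2), quality of life (6.3.1), scintigraphy (6.3.3), and safety laboratory values, vital signs and ECG (7.3 to 7.5).

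**The concern.** A subject who leaves 4 months after the last injection has an EOS Visit then. A subject who completes has an EOS Visit at Month 24. If the database holds both as the same visit, SAP 4.4 puts both in one row, although the elapsed times differ by 20 months. The SAP 7.3 to 7.5 exclusions of unscheduled visits do not catch this, because an early EOS Visit is required by the protocol.

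What is at stake is how the last row of each by-visit table is read. By-time-point description is the only planned analysis of the secondary endpoint as a whole. Measures such as UACR, iPTH, potassium and haemoglobin have no slope model to fall back on. With at most 10 subjects, one early leaver is 10% or more of the row.

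**Working it through.** The plan states no figure to reproduce. There is no test ("no statistical hypothesis testing is planned for the study") and no sample-size calculation ("Up to 10 subjects who complete screening procedures and satisfy all inclusion and exclusion criteria will be enrolled"). The arithmetic below only illustrates the possible size.

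**Inputs from the documents**
- N: at most 10 (SAP 9).
- Follow-up: 24 months after the last injection (SAP 3.1: "Subjects will be followed over a 24 month period post the last injection").
- Injections 6 months apart (SAP 3.1), so Month 24 is T = 6 + 24 = 30 months after the first injection. Baseline is the last value before that injection (SAP 4.7).

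**Assumptions (the documents give no figures)**
- Linear eGFR decline; completers lose s = 2 to 4 mL/min/1.73m² per year.
- k = 2 to 4 of 10 leave early, at t = 9 to 24 months after the first injection, before dialysis.
- Leavers decline r = 1 to 3 times as fast as completers.
- Everyone else has two injections and reaches Month 24.

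**Formulas (mean change from baseline)**
- Completers only: C = −s × 30/12
- Pooled row: P = [(10 − k) × C − k × r × s × t/12] / 10
- All 10 at a true Month 24: A = [(10 − k) × C − k × r × s × 30/12] / 10
- P − A = (k/10) × r × s × (30 − t)/12, which is positive whenever t < 30
- P − C = (k/10) × s × (30 − r × t)/12, which changes sign at r = 30/t

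**Equal slopes (r = 1), leaving 6 months after the last injection (t = 12)**
- k = 3, s = 2: C = A = −5; P = (7 × −5 + 3 × −2)/10 = −4.1, an understatement of 0.9.
- k = 3, s = 4: C = A = −10; P = (7 × −10 + 3 × −4)/10 = −8.2, an understatement of 1.8.
- In relative terms, (k/10) × (30 − 12)/30: 0.3 × 0.6 = 18% for three leavers, and 0.2 × 0.6 = 12% for two.

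**Unequal slopes (s = 3, k = 3, C = −7.50)**

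| t (months) | r | Pooled row P | All 10 at true Month 24, A | P − C |
|---|---|---|---|---|
| 12 | 1 | −6.15 | −7.50 | +1.35 (milder) |
| 12 | 2 | −7.05 | −9.75 | +0.45 (milder) |
| 18 | 2 | −7.95 | −9.75 | −0.45 (steeper) |
| 24 | 2 | −8.85 | −9.75 | −1.35 (steeper) |

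The slope ratio at which the pooled row equals the completers-only row is 30/t: 3.33 at 9 months, 2.50 at 12, 1.67 at 18 and 1.25 at 24.

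Over the grid s = 2, 3, 4; k = 2, 3, 4; t = 9, 12, 18, 24; r = 1, 1.5, 2, 3, P − A runs from +0.2 to +8.4 and P − C from −5.6 to +2.8 mL/min/1.73m². The extremes are upper bounds. From an entry eGFR of 14 to 20, a loss of 10 already leaves 4 to 10, within the kidney-failure stage of Protocol Table 4. Many such subjects could have started dialysis, and SAP 6.2 would then drop their later values.

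**The case against.** **Pooling is not shown to happen.** The case report form and database visit labels are not in the documents. If early termination has its own label, SAP 4.4 keeps the two apart. This stands, and it makes the point conditional. It does not remove it: every description of the visit gives it one name, and no SAP rule separates the two uses.

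**The direction is not fixed.** A reader might infer that the pooled row always flatters late kidney function. That holds against the unobserved value with all subjects followed to Month 24, if decline continues. It does not hold against completers only, the row that a separate early-termination category would leave: fast decliners who leave late make the pooled row look worse. For vital signs, ECG and the left–right split on scintigraphy, no steady decline is implied at all.

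**This is not last observation carried forward.** A reader might infer a breach of SAP 4.5. The early EOS value is actually observed, and missed visits in between stay missing. The problem is the time under which the value is filed, though a missing Month 24 value may no longer appear as missing.

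**Much of the plan is untouched.** The eGFR slope models use study day, as do the subject plots of eGFR, creatinine, urine albumin and urine protein (SAP 6.3.4). Time to dialysis uses dates (6.3.5). Shift tables take the worst value (7.3). Efficacy summaries already drop post-dialysis values, although SAP 7.3 states no such exclusion for the safety laboratory tables. Scintigraphy in early leavers is at the investigator's discretion (Protocol 6.6). Listings and the disposition table (SAP 5.1) would let a careful reader trace early leavers. All of this stands and limits the point to the by-visit tables.

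**Conclusion.** The point holds as a gap in SAP 4.4. Applied as written to a visit with two meanings, the rule lets early-termination values into the Month 24/EOS row, and a row that mixes follow-up times is not a 24-month result.

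Confidence is high that the visit has two meanings and that no rule separates them. It is only moderate that pooling would occur, because the database labels are not shown.

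The size is illustrative: an understatement of 12% to 18% against all subjects seen at Month 24, if 2 or 3 of 10 leave 6 months after the last injection with the same slope as the rest. The documents support no fixed direction against completers. No hypothesis test is affected. The consequence is for the reading of one row in descriptive tables, but that row closes the follow-up window of the secondary endpoint. It should be settled before database lock.

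**What to change.** Add to SAP 4.4:
- An EOS Visit held before the Month 24 window opens (Month 24 minus 7 days, from the ±7 days in Protocol 6.5) is tabulated in a separate Early Termination row. Alternatively, it is mapped to the scheduled visit nearest in days since the last injection, with a rule for when that visit already has a value.
- The Month 24 row and its n include only Month 24 assessments.
- Early-termination values stay in the slope models, shift tables and listings.

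If the database already separates the two occasions, one sentence saying so, plus the restriction on the Month 24 row, is enough.

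The cost is a few sentences and one derived visit variable, with no new data. The downside is a smaller Month 24 n and a row made up of completers. Label it as completers only, because those subjects may be a selected group.

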4.5 Handling of Dropouts or Missing Data

Missing data will remain missing. No imputation of missing data will be performed.

4.6 Multiple Comparisons

No multiple comparisons are planned for the study.

4.7 Baseline Definition

Unless otherwise specified, baseline is defined as the last non-missing value prior to the first REACT injection.

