- h. Vital signs (included are heart rate, blood pressure, and respiration rate) will be measured throughout the procedure. Temperature is not required to be recorded throughout the procedure.
- i. Refer to [Table 2](#) for a schedule of laboratory assessments.
- j. Ultrasound will be performed at the Screening Visit to verify subject eligibility and to obtain baseline echogenicity reading. Subsequent Ultrasounds will monitor echogenicity.
- k. Ultrasound will be performed following the in-patient renal biopsy on Day 0 and Day 1, and following the in-patient REACT injection(s) on Day 0 and Day 1 with the aim of monitoring possible, subclinical AEs.
- l. A MRI study without contrast will be performed at the Screening Visit through Day -1 before renal biopsy to determine kidney size and volume.
- m. Renal scintigraphy will be performed before the first REACT injection, before the last REACT injection, at the 6-Month Visit after the last REACT injection, at the 12-Month Visit after the last REACT injection, and at the month 24/EOS Visit.
- n. The REACT preparation will be handled and injected according to procedures described in the Study Reference Manual.
- o. CT Scan must be used in conjunction with ultrasound for the REACT injection procedure.
- p. Subjects may be admitted to hospital per site standard practice. Subjects who do not experience complications may be discharged the same day consistent with site standard practice.
- q. Subjects will undergo a funduscopic exam with retinal photography of both retinae to monitor diabetic retinopathy at screening, month 12, and month 24/EOS visit.

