**Figure 2: Serum Creatinine Pre- and Post-REACT Treatment (RMTX-CL001)**

### 1.5.1. Kidney Cortical Thickness

Patients suffering from chronic kidney disease undergo a thinning of the functional portion of the kidney, i.e., the cortex. Renal cortical thickness is reduced in CKD as a result of fibrosis and

scarring as the disease progresses. An increase in cortical thickness was associated with kidney regeneration in pre-clinical studies of REACT and was confirmed histologically in all 4 animal species studied (refer to the [Investigator's Brochure](#)). In the clinical trials TNG-CL010 and TNG-CL011, cortical thickness was evaluated using imaging technologies; no biopsies were taken to confirm the basis for the increased thickness. Cortical thickness was measured in both the right and left kidney to determine if the implanted left kidney exhibited any change in cortical thickness that could be attributed to REACT implantation. The right kidney served as a non-implanted control.

On average, cortical thickness increased in the left kidney from 14 mm at baseline to approximately 16 mm after one year of REACT treatment. This change in cortical thickness was not sufficient to cause an increase in the total volume of the left kidney (data not presented). No change in cortical thickness was observed in the right kidney cortex.

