## 7.4. Renal Imaging

### 7.4.1. Ultrasound

Renal ultrasound will be performed at the Screening Visit to verify subject eligibility (i.e., no evidence of renal tumors, polycystic kidney disease, renal cysts or other anatomic abnormalities that would interfere with the REACT injection procedure) along with obtaining a baseline echogenicity reading. Ultrasound will also be performed following the in-patient renal biopsy on Day 0 and Day 1 and following the in-patient REACT injection(s) on Day 0 and Day 1 with the aim of monitoring possible, subclinical AEs. Findings from the ultrasound (e.g., resistance index, length, etc.) will be recorded on the CRF. An ultrasound may be conducted at other times, in the judgment of the Investigator, if needed for additional safety evaluation(s).

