6.3.2 Renal Ultrasound

The actual and change from baseline values for the renal ultrasound measurements of cortical thickness, length, and volume for the treated and untreated kidney will be summarized descriptively at each time point post REACT injection using the IAS.

Measurements taken after dialysis has started will be removed from all efficacy analyses. All renal ultrasound measurements will be presented in a data listing for the FAS. The listing will include a notation for assessments taken after the start of dialysis so that it is clear which records are included in the efficacy analyses.

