7.4 Vital Signs

Vital signs are taken throughout the procedure during biopsy and first/second REACT injections. As peri-procedure vital signs will be impacted by the procedure (e.g., sedation), the baseline value for all vital signs will be defined as the last non-missing value taken on a date *prior* to the date of first REACT injection. Diastolic and systolic blood pressure measurements are taken in triplicate at the pre-biopsy visit (Day -3 to Day -1), and the pre-injection visit (Day -14 to -10). The average of the blood pressure measurements will be used analysis purposes. For example, in most cases, the baseline blood pressure will come from the pre-injection visit (Day -14 to -10). In those cases, the baseline will be set to the average of the measurements taken for that visit.

Descriptive summaries of the vital signs (both raw and change from baseline values) including systolic and diastolic blood pressure, heart rate, respiratory rate, body temperature, weight and BMI will be prepared by visit using the IAS. A listing of all the vital sign measures will also be provided for the FAS.

Vital sign results from unscheduled visits will be excluded from table summaries but will be included in data listings. Additionally, measures taken during procedures will not be summarized, only listed.

If there is a difference between the IAS and FAS, then summaries conducted using the IAS will

be repeated using the FAS.

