12. APPENDICES

12.1 Appendix A: Time and Events Table

Abbreviations: AE (adverse event); ConMeds (concomitant medications); DSMB (Data Safety and Monitoring Board); ECG (electrocardiogram); EOS (End-of-Study Visit); I/E (inclusion /exclusion); KDQOL (Kidney Disease Quality of Life Survey); MRI (magnetic resonance imaging); REACT (Renal Autologous Cell Therapy); PE (physical examination).

Notes:

- * Day 1 follow-up visit should only be conducted if there is a safety event identified during or after the kidney biopsy.
- ** Every attempt should be made to ensure the second REACT injection is administered 6 months (+4 weeks) after the first injection. In the event that the subject cannot schedule his/her second REACT injection 6 months after receiving the first injection or cannot keep his/her scheduled 6-month visit, ProKidney and the Medical Monitor must be notified immediately. The expectation is that the subject and the clinical center will accommodate the Sponsor's preference that the series of 2 REACT injections should be administered no more than 6 months apart.
- a. If the screening assessment falls outside of the 60-day window before renal biopsy, re-screening will be performed as described in Screening ([Section 6.1](#)).
- b. Because the second REACT injection will occur 6 months (+4 weeks) after the first injection, the 6-month visit may not be scheduled.
- c. In the event that a second REACT injection will not be administered, the subject will undergo all follow-up assessments after the last REACT injection at the 24-month EOS Visit.
- d. The EOS Visit will take place 24 months after the last REACT injection, or when the subject is terminated from the study by the Investigator ([Section 8.6](#)) or when the subject voluntarily discontinues from the study ([Section 5.4](#)).
- e. The Informed Consent Form must be signed and dated prior to conducting any study-specific procedures, including those at the Screening Visit. Signing the Informed Consent Form starts the 60-day timeline for screening.
- f. The PE and interim PE are described in [Section 7.2.2](#).
- g. Vital signs include heart rate, resting blood pressure, respiration rate, and body temperature. ([Section 7.2.1](#)). At the Pre-Biopsy Visit (Day -3 to Day -1) and the Pre-Injection Visit (Day -14 to Day -10) three BP measurements will be taken and the average will be used to satisfy entry criteria.

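### The SAP does not exclude post-biopsy scans from the ultrasound baseline, so a procedure-affected scan could become the treated kidney's starting point in some subjects

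*SAP*

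**What the plan says.** - **Baseline rule.** SAP 4.7: "Unless otherwise specified, baseline is defined as the last non-missing value prior to the first REACT injection".
- **Endpoint.** SAP 6.3.2 summarises "The actual and change from baseline values for the renal ultrasound measurements of cortical thickness, length, and volume for the treated and untreated kidney" at every time point after injection, in the injection analysis set. It names no baseline.
- **Scans before the first injection.** Protocol Table 1, note j: "Ultrasound will be performed at the Screening Visit to verify subject eligibility and to obtain baseline echogenicity reading". Protocol 7.4.1: "Ultrasound will also be performed following the in-patient renal biopsy on Day 0 and Day 1". SAP Appendix A, note k, repeats this: "Ultrasound will be performed following the in-patient renal biopsy on Day 0 and Day 1". The stated purpose of these later scans is to detect adverse events that cause no symptoms.
- **Day 1 after biopsy.** The starred note in SAP Appendix A makes that visit conditional: "Day 1 follow-up visit should only be conducted if there is a safety event identified during or after the kidney biopsy".
- **What is recorded.** Protocol 7.4.1 sends ultrasound findings to the CRF, naming resistance index and length as examples. It does not separate the Screening scan from the post-procedure scans.
- **An existing exception.** SAP 7.4 overrides the general rule for vital signs and begins its reason with: "As peri-procedure vital signs will be impacted by the procedure (e.g., sedation". There is no matching override for ultrasound.
- **Safety ultrasound.** SAP 7.7 tabulates abnormalities by visit, with its own listing.
- **Use of the other kidney.** Protocol 1.5.1, on the earlier clinical trials: "The right kidney served as a non-implanted control".

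**The concern.** The general rule picks whichever usable value lies closest before the first injection. In the schedule as described, the scans closest to injection are those made straight after the biopsy, on the kidney that will be treated. Protocol 1.7 lists haematoma and subcapsular bleeding among the biopsy risks, and Protocol 1.7.1 calls haemorrhage the most common adverse event of a kidney biopsy. A change of this kind affects one kidney only.

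Two things are at stake. First, an enlarged baseline lowers the apparent change in the treated kidney and leaves the untreated kidney as it was, so the side-by-side comparison is distorted. Second, the baseline may not be the same kind of scan in every subject, which matters in a study of at most 10 subjects.

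**Working it through.** The plan gives no figure to reproduce here. The check is to put the scans in order, apply the rule, and see what an enlarged baseline would do.

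**1. Which rule applies.** SAP 6.3.2 is silent on baseline and SAP 7.4 concerns vital signs only, so SAP 4.7 governs.

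**2. Order of scans in the text.**
- Screening scan, before biopsy (Protocol 6.1 and 7.4.1).
- Post-biopsy scans on Day 0 and Day 1 (Protocol 7.4.1).
- First injection about one month after biopsy (Protocol 6.2), into the biopsied kidney (Protocol synopsis, REACT Injection).
- The descriptions of the visit 10 to 14 days before injection (synopsis, Protocol 4.2 and 6.3) mention examination, eligibility review and scintigraphy, but no ultrasound.

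**3. What SAP 4.7 then selects.**

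| Situation | Baseline scan |
|---|---|
| Post-biopsy scans carry the measurement; Day 1 scan done | Day 1 after biopsy |
| Post-biopsy scans carry the measurement; no Day 1 scan | Day 0 after biopsy |
| Post-biopsy scans held only as safety ultrasound | Screening |
| Subject biopsied earlier in RMCL-002, not biopsied again (Protocol 5.4) | Screening |

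The first two rows are the problem. The last row shows that a mixture is possible even if every biopsied subject is handled alike. If the Day 1 visit is held only after a safety event, as the starred note says, Day 1 baselines would come from the subjects most likely to have a procedure effect. Note k lists the Day 1 scan without that condition, so the two notes need reconciling.

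**4. Direction and size.** Let d be the enlargement of the treated kidney on the baseline scan.

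Observed change = true change − d.

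For scale, Protocol 1.5.1 reports mean cortical thickness in the implanted kidney going from 14 mm to about 16 mm: 16 − 14 = 2 mm, with no change on the other side. The documents give no value for d, so the values below are assumptions.

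| d (mm, assumed) | Observed change (mm) | Share of 2 mm hidden |
|---|---|---|
| 0 | 2.0 | 0% |
| 0.5 | 2 − 0.5 = 1.5 | 0.5/2 = 25% |
| 1.0 | 2 − 1.0 = 1.0 | 1.0/2 = 50% |
| 2.0 | 2 − 2.0 = 0 | 2.0/2 = 100% |

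If only m of n subjects have a post-biopsy baseline, the mean is understated by (m/n) × d. With 5 of 10 subjects and d = 1.0 mm (both assumed), that is 0.5 × 1.0 = 0.5 mm, or 25% of 2 mm.

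**5. Treated minus untreated.** For one subject the contrast is (treated change − d) − untreated change = true contrast − d. Pairing alone does not remove the distortion, so the baseline has to be settled first. When the same subjects are measured on both sides, the mean contrast can be read from the two columns. Its spread cannot, because

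Var(difference) = Var(treated) + Var(untreated) − 2 Cov(treated, untreated),

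and separate summaries do not report the covariance.

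**The case against.** The strongest reply is that the SAP already keeps two kinds of ultrasound data: measurements in 6.3.2 and safety abnormalities in 7.7, each with its own listing. The post-biopsy scans have a safety purpose. If they are stored only as safety ultrasound, SAP 4.7 picks the Screening scan and nothing goes wrong. This may be what the sponsor intends, but neither document defines safety ultrasound or says that such scans are kept out of 6.3.2. A length recorded on a post-biopsy scan would meet the wording of 4.7.

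Other parts of the reply stand and limit the point:

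- A reader might infer that the baseline definitely is the post-biopsy scan. The documents do not show that. Only length is named among these measurements as an ultrasound CRF finding; cortical thickness and volume on post-biopsy scans are not documented. SAP 5.3 says volume comes from MRI and CT, which itself needs reconciling with the ultrasound volume in 6.3.2. I had only the notes to the visit grids in Protocol Table 1 and SAP Appendix A, so a later pre-injection scan cannot be ruled out.
- A reader might take the protocol to name the Screening scan as baseline for these measurements. It does so only for echogenicity. SAP 5.3 does use screening values, but for a characteristics table, and takes thickness from MRI first.
- A reader might fear a false benefit. An enlarged baseline works the other way, against REACT.
- Protocol 1.7.1 expects limited damage from a properly targeted biopsy, so d may be small.
- The paired contrast is an addition, not a correction of an error. The protocol's account of the earlier trials also reports the two kidneys side by side. No particular gain in precision can be claimed, since the documents give no correlation between kidneys.

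**Conclusion.** The concern holds as a gap in the specification. The general baseline rule reaches the ultrasound measurements without exception, and nothing in the text stops a post-biopsy scan of the treated kidney from being selected. Different subjects could therefore start from different kinds of scan. The SAP recognised the same kind of problem for vital signs and dealt with it there.

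The size is unknown. The 25% to 50% illustration depends wholly on an assumed inflation of 0.5 to 1.0 mm, on thickness being measured at the post-biopsy scan, and on the earlier 2 mm change as the yardstick. The result would be an understated gain, or an apparent loss, in the treated kidney. The endpoint is exploratory and descriptive, so the consequence is confined to how these ultrasound results are read. The primary endpoint and the secondary laboratory endpoints are untouched.

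**What to change.** In SAP 6.3.2, add:

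> For ultrasound cortical thickness, length and volume, baseline for both kidneys is the last scan before biopsy (the Screening scan). Scans made after the biopsy, and on Day 0 and Day 1 of either injection, are reported only under Section 7.7.

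Include a clause for subjects biopsied under RMCL-002, whose Screening scan in this study comes after their biopsy: name that Screening scan as their baseline and mark these subjects in the listing. The restriction on injection-day scans is needed because 6.3.2 covers every time point after injection, and Protocol 6.4 uses the day-after scan to look for swelling and fluid. Reconcile note k with the conditional Day 1 visit, and the ultrasound volume in 6.3.2 with the sources named in 5.3.

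As a descriptive addition, report the per-subject treated-minus-untreated difference in change at each time point, with a 95% CI. The untreated kidney is the only concurrent control in this single-arm study, and an interval given as description does not conflict with the absence of hypothesis tests.

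The cost is a few sentences and one derived variable, with no new data. If the sponsor already handles the scans this way, the amendment only writes it down.
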